1.0 OBJECTIVES OF STUDY

1.1 Primary Objective

In patients with metastatic, estrogen receptor (ER) negative, progesterone receptor (PR) negative, and human epidermal growth factor receptor 2 (HER-2-Neu) negative breast cancer (called triple negative breast cancer or TNBC), we will:

- Characterize the safety profile and treatment tolerance of Veliparib (ABT-888) in combination with Lapatinib (Tykerb).

1.2 Secondary Objectives

In patients with metastatic TNBC, who will be treated with the combination of Veliparib and Lapatinib, we will:

- Estimate the objective response rate (ORR) (complete responses [CRs] plus partial responses [PRs]);
- Determine progression free survival (PFS);
- Correlate pre-treatment tumor gene expression profile, biomarkers of DNA repair (H2AX, BRCA localization), EGFR location and signaling, and apoptosis markers with the ORR and PFS;
- Correlate serial measures of circulating tumor cells (CTCs) and serum levels of M30 with the ORR and PFS.
- Determine the pharmacokinetics of Veliparib and Lapatinib when given in combination.

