The primary endpoint of the trial is safety of the combination of Lapatinib and Veliparib. Objective response rate (ORR) and progression free survival (PFS) will be secondary endpoint. Patients will be evaluated for response every 2 cycles (8 weeks) using the RECIST 1.1 criteria (see Appendix D); patients with stable disease, PR or CR may continue therapy until disease progression or intolerance to the combination. Patients with progressive disease (PD) at any time will go off the study. The total enrollment goal is 20 patients; patients will be enrolled in a single site (University of Alabama at Birmingham) over a projected 12-18 months accrual interval. A biopsy of an accessible metastatic lesion will be obtained in appropriate patients (see inclusion criteria). Tissue obtained in this trial will be analyzed for global gene array analysis or other comprehensive genomic analysis (“Next-Gen” genomic analysis) at UAB and HudsonAlpha Institute for Biotechnology, and immunohistochemistry (ER, PR, HER2, Ki67), biomarkers of DNA repair such as H2AX and BRCA localization, EGFR location and signaling, and apoptosis markers; data obtained from the biopsies will be correlated with ORR and PFS. Plasma DNA and serum levels of M30 will be obtained and correlated with the efficacy data. Adverse events (toxicity) will be assessed continuously while the patient is in active therapy with appropriate adjustments of Lapatinib and Veliparib doses as described above. The protocol will be approved by the UAB Institutional Review Board (IRB).

Figure 7: Treatment Plan

[figure not shown]

Table 1

Pre-study Evaluation (Section 4)	Therapy (Section 6)	Follow-up

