Pharmacogenomic Analyses – Blood samples for pharmacogenomic analyses will be collected on a first day before initiation of research agents. Blood will be collected into one 6 ml K₂EDTA polypropylene blood collection tube (Becton-Dickinson) and into one PAX gene tube. The 6 mL polypropylene K₂EDTA tube will be placed in an ice bath immediately following collection and stored upright in a freezer set at -20°C (+/- 10°C) until sending to the laboratory. It is important to collect a full tube of whole blood. The PAX gene tube should be stored upright at room temperature for a minimum of 2 hours or a maximum of 4 hours before processing or transferring to a freezer. They should be stored upright in a wire rack and stored at -20 degrees Celsius or colder until sending to the laboratory. Blood samples should be sent to The University of Alabama (Attention: The University of Alabama at Birmingham; Center for Clinical Translation Science (CCTS) Laboratory, [name]) as soon as logistically possible following blood draws. The University of Alabama will store the samples until assays are to be performed. Samples will be shipped to The HudsonAlpha Institute for Biotechnology. The Hudson Alpha Institute may conduct pharmacogenomic assays possibly including, but not limited to, DNA sequencing of exons as well as DNA sequencing from RNA transcripts, DNA methylation screens, and tests for specific single nucleotide polymorphisms. These tests on normal tissue may provide reference values for comparison against similar tests previously approved for the patients' tumor tissue. The protocol will provide the tubes (EDTA and PAX gene tubes).

Plasma Tumor DNA (ptDNA)-

Successful treatment depends on the ability to monitor disease burden and response to therapies. Recently, a proof of principle study has shown that plasma tumor DNA (ptDNA) can be used as a reliable breast cancer biomarker in metastatic disease, due to its sensitivity and wide dynamic range. ptDNA more accurately reflects changes in response to therapies, and absolute levels of ptDNA

demonstrate prognostic significance. Thus, ptDNA as a liquid biopsy shows great promise in the clinical management of metastatic breast cancer. The key is to maximize removal of contaminating cells and genomic DNA from these cells as large genomic DNA fragments hinder plasma DNA analysis.

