It is now well-established that cells naturally secrete or shed small DNA fragments into the circulation with most of this DNA being compartmentalized in the plasma component of whole blood. Small amounts of cell-free circulating DNA can be detected in plasma from healthy individuals,^{79,80} is often highly elevated in metastatic cancer patients^{79,81} and correlates with disease burden.^{78,82,83} Interestingly, how ctDNA enters the plasma is not precisely known. While the fragment size of circulating DNA in healthy individuals suggests that it originates from apoptotic cells,⁸⁰ circulating DNA is also shed from non-apoptotic cells and in this instance it is often larger and more variable in size.^{84,85,86} For clarity, we prefer and will henceforth use the term plasma tumor DNA (ptDNA) over ctDNA since there is confusion regarding ctDNA versus DNA derived from CTCs, which are distinctly different. In addition, ptDNA is more specific as it is a subset of ctDNA, since ctDNA also includes urine tumor DNA (utDNA) as well as ctDNA in other bodily fluids. Recent work, including that from our own group, supports the utility of ptDNA as a facile means for liquid biopsy.^{78,81,87} [name]'s group and others have shown that cancer specific somatic mutations can be detected in ptDNA from metastatic breast cancer patients with up to a 100% concordance when blood is taken concurrently with tissue biopsy.^{78,81,87} In contrast, [name] group also demonstrated that mutational discordance can occur between ptDNA and primary breast cancer tissues when there is a prolonged period (greater than 3 years) between initial diagnosis and recurrence.⁸⁷ This speaks to the now proven concept of tumor heterogeneity and clonal evolution. ptPtDNA has also been used to identify treatment associated mutational changes.^{77,81} Thus, assessment of ptDNA can relay the mutational status of a patient's cancer with the ability for serial testing.

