Blood will be collected in three cell-free DNA BCT tubes (Streck) per time point: at baseline before drug administration, on days 15 and 29 (day 1 of cycle 2 pre-treatment). Samples collected in the DNA BCT tubes are stable for up to 14 days at temperatures between 6-37° C. Once tubes are filled completely the tube should be mixed by gently inverting 8 to 10 times. The tubes will be transferred to [name] lab for processing and freezing of the samples which will be batched and sent at a later date for analysis to [name]'s lab at the Sidney Kimmel Comprehensive Cancer Center, Johns Hopkins University.

Serum Marker of Apoptosis - Serum levels of M30 will be drawn pre-dose, Day 8, and Day 15 of cycle one only. The changes of the serum levels of M30 at each time point will be correlated with levels of M30 in CTCs as well as with efficacy parameters. M30 serum evaluations will be conducted at the Mayo Clinic by [name]. Activation of the intrinsic apoptotic pathway involves release of cytochrome c to the cytosol, activation of caspases (specifically caspase 9 followed by caspase 3), and cleavage of hundreds of substrates by caspase 3.^{72,73} Among the caspase 3 substrates is cytokeratin 18, which yields a fragment that is uniquely detectable using the monoclonal antibody M30 upon caspase cleavage.⁷⁴ When apoptotic cells lyse, all of these proteins (cytochrome c, cleaved/activated caspase 3 and cleaved cytokeratin 18) are released to the circulation, where they can be detected by ELISA to provide an assessment of the degree of epithelial cell apoptosis. Samples will be sent to Mayo Clinic for later analysis. No funding is necessary to conduct the evaluation in the laboratory; funds are needed only for shipping.

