7.0 STATISTICAL CONSIDERATIONS

This is an open-label, single arm, single institution, pilot clinical trial. The primary objective is to characterize the safety profile and treatment tolerance of Veliparib (ABT-888) in combination with Lapatinib (Tykerb) in patients with metastatic, estrogen receptor (ER) negative, progesterone receptor (PR) negative, and human epidermal growth factor receptor 2 (HER-2-Neu) negative breast cancer. Secondary objectives will estimate the objective response rate (ORR) (complete responses [CRs] plus partial responses [PRs]); Determine progression free survival (PFS); correlate pre-treatment tumor gene expression profile, biomarkers of DNA repair (H2AX, BRCA localization), EGFR location and signaling, and apoptosis markers with the ORR and PFS; Correlate serial measures of CTCs and serum levels of M30 with the ORR and PFS and determine the pharmacokinetics of Veliparib and Lapatinib when given in combination. A total of 20 (maybe 25 if an additional cohort is added) patients will be enrolled in a single site (University of Alabama at Birmingham) over a projected 12-18 months accrual interval.

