7.2 Secondary Endpoint

In patients with metastatic TNBC, who will be treated with the combination of Veliparib and Lapatinib, we will estimate the ORR (CRs plus PRs); determine PFS; correlate pre-treatment tumor gene expression profile, biomarkers of DNA repair (H2AX, BRCA localization), EGFR location and signaling, and apoptosis markers with the ORR and PFS; correlate serial measures of CTCs and serum levels of M30 with the ORR and PFS; determine the pharmacokinetics of Veliparib and Lapatinib when given in combination.

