7.5.2 Analysis of Efficacy endpoints

At the completion of the study, the secondary endpoint of ORR rate will be estimated along with two-sided 95% confidential intervals for Lapatinib and Veliparib combination group with exact method of [Clopper-Pearson intervals](#). Secondary endpoint analysis will be descriptive. Mean, median, and range will be used to describe continuous demographic variables. Frequency and proportion will be used to describe categorical variables. The K-M estimator will be used to estimate median progression free survival along with 95% confidence intervals.

Exploratory analysis will be conducted on the correlations between clinical outcomes and biomarkers or gene expression profiles. Gene expression profile, proliferation/apoptosis markers, and circulating level of tumor cells will be analyzed between responders and non-responders using two-sample t-test test assuming normal distribution for gene expression level. An appropriate normal transformation will be conducted prior analysis when it is necessary. Alternatively, one way analysis of variance (ANOVA) can be used to evaluate gene expression and biomarkers by responders. Logistic regression analysis will be used to predict response with these genes or biomarkers with or without adjustment for covariate, e.g. age. Two-sample log rank test will be used to compare PFS curves classified by biomarkers or gene expression profiles so that potential prognostic biomarkers or genes will be identified. Multivariate Cox proportional hazards model will be used to identify a set of biomarkers for prediction of time to disease progression between responders and non-responders. Hazards ratios with 95% confidence intervals will be calculated for each significant biomarker in terms of predicting time to disease progression. Since this is an exploratory pilot study which will be used as a hypothesis generator. We will include EGFR expression and location, and markers of apoptosis and DNA repair as covariate in all above

exploratory analysis.

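### CTCs are analysed but never collected, Cycle 2 pharmacokinetics is described inconsistently, and veliparib AUC to the last sample runs across a second dose

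*Combined protocol and SAP*

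**What the plan says.** **CTCs.** Section 1.2 lists "Correlate serial measures of circulating tumor cells (CTCs) and serum levels of M30 with the ORR and PFS". Section 7.0 restates it ("Correlate serial measures of CTCs and serum levels of M30 with the ORR and PFS and determine the pharmacokinetics"), as does Section 7.2 ("correlate serial measures of CTCs and serum levels of M30 with the ORR and PFS"). Section 7.5.2 gives it a test: "Gene expression profile, proliferation/apoptosis markers, and circulating level of tumor cells will be analyzed between responders and non-responders". Under the serum apoptosis marker, Section 6.3 adds: "The changes of the serum levels of M30 at each time point will be correlated with levels of M30 in CTCs". By contrast, Section 3.0 names only plasma DNA and M30: "Plasma DNA and serum levels of M30 will be obtained and correlated with the efficacy data".

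**PK by cycle.** Section 7.5.3 says descriptive statistics of the non-compartmental parameters will be produced for Cycle 1 and Cycle 2, and allows an optional plot of pre-dose concentrations over Weeks 1-5. Section 6.3 places PK in the first course, on Days 1-3 and 8-10, and footnote 4 of Section 6.6 gives the same days. The 6.6 table marks PK in the column for the first day of every cycle and in the Day 8 column.

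**Veliparib AUC.** Sections 3.0 and 5.1.5 dose veliparib every 12 hours from Day 2. Section 6.3 samples at 0.5, 1, 2, 4, 6, 8 and 24 hours after the Day 2 dose. Section 7.5.3 lists AUC to the final collection point, dose-interval AUC, AUC to infinity and half-life, and permits compartmental or population modelling if warranted. It gives no rule on which points enter the terminal slope.

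**The concern.** Each part is an analysis that the sampling plan does not support as written.

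Without a CTC collection, part of a stated secondary objective has no data, and neither does the planned correlation with M30 in CTCs.

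For PK, the analyst is told to summarise a cycle that Section 6.3 does not sample.

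For veliparib, PK of the combination is a secondary objective and the pilot is meant to inform a phase II design. An AUC that mixes one fully sampled dose with a second, unsampled one is not an exposure that design can use. Because no slope rule is written, two analysts could also report half-lives several-fold apart from the same samples.

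**Working it through.** The plan states no figure to reproduce for this point. The first two parts are comparisons of text; the third needs arithmetic.

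**1. CTC analyses against collection.** The blood collections in Section 6.3, the 6.6 schedule and Appendix E are: PK; serum for microRNA and M30; pharmacogenomic blood; and ptDNA tubes at baseline, Day 15 and Day 29. CTC collections: 0. The ptDNA tubes do not fill the gap. Section 6.3 says of that assay "The key is to maximize removal of contaminating cells and genomic DNA from these cells", and separates the analytes itself: "there is confusion regarding ctDNA versus DNA derived from CTCs, which are distinctly different". Serum M30 is drawn pre-dose and on Days 8 and 15, so that half of the objective stands.

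**2. PK by cycle.**

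| Source | Cycle 1 | Cycle 2 |
|---|---|---|
| 6.3 and 6.6 footnote 4 | Days 1-3 and 8-10 | none listed |
| 6.6 table mark | Day 1, Day 8 | Day 1, if read literally |
| 7.5.3 | parameters planned | parameters planned |

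On the Section 6.3 days, pre-dose samples fall in Weeks 1 and 2 only; the optional plot refers to Weeks 1-5.

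**3. Veliparib AUC to the last sample.** Inputs from Section 2.5: Tmax 1-2 h; half-life 4-5 h (Phase 0 study) to about 6 h. Assumptions: one compartment with first-order absorption, and a second dose at 12 h.

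With single-dose AUC to infinity scaled to 1:

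- C(t) = ke·ka/(ka − ke) × (exp(−ke·t) − exp(−ka·t)), with ke = ln 2 / half-life, and ka solving ln(ka/ke)/(ka − ke) = Tmax.
- Two-dose concentration = C(t) + C(t − 12).
- AUClast = trapezoid over 0, 0.5, 1, 2, 4, 6, 8 and 24 h.

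Example, half-life 5 h and Tmax 2 h: the concentrations at 8 and 24 h are 0.0515 and 0.0352. The 8-24 h trapezoid is (0.0515 + 0.0352)/2 × 16 = 0.694. Total AUClast is 1.314. The true 0-24 h AUC is 0.960 for one dose and 1.746 for two, so the ratios are 1.314/0.960 = 1.37 and 1.314/1.746 = 0.75.

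Over Tmax 1, 1.5 and 2 h, half-life 4, 5 and 6 h, and both linear and linear-up/log-down trapezoids:

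| Second dose at | AUClast / one-dose 0-24 h | AUClast / two-dose 0-24 h |
|---|---|---|
| 12 h | 1.30-1.37 | 0.69-0.77 |
| 10 h | 1.23-1.31 | 0.64-0.71 |
| 14 h | 1.39-1.45 | 0.76-0.85 |

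No ratio reaches 1.

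**Slope, conditional on analyst choice (second dose at 12 h).** If the 24-hour point is used with the last three or four points, apparent half-life is 12.6-31.8 h and AUC to infinity is 1.75-3.09 times true. If it is left out (slope on 4, 6 and 8 h), half-life is 4.0-6.1 h and AUC to infinity is 0.99-1.00 of true, with 27-44% of it extrapolated.

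**After the fix.** First-dose 0-12 h AUC, with 8-12 h extrapolated on the 4, 6 and 8 h slope, is 0.99 of true, and 16-22% of it is extrapolated. At steady state, with the gap between evening and morning dose varied from 10 to 14 h, the same rule gives 0.95-1.05 of true.

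These ratios contain no measurement error. With an assumed 10% error per sample, an individual's half-life from those three points has a 5th-95th percentile range of roughly 0.67-2.1 times true, because the points span only 4 hours, at most one half-life.

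**The case against.** **Cycle 2 PK may be intended.** The 6.6 mark sits under the first day of every cycle and carries footnote 4, which describes serial sampling and not a single trough. A reader might infer from Section 6.3 that Cycle 2 parameters are simply impossible. The documents do not support that much: they conflict. Cycle 1 only is the likelier reading, because Section 6.3 says so, footnote 4 lists no Cycle 2 day, and the same column holds pharmacogenomics, which footnote 9 limits to Cycle 1 Day 1. The sponsor has to settle it.

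**Appendix E.** A reader might take the section D heading, which groups PK with microRNA and M30 serum, as evidence of a Day 29 PK sample or of a clash with footnote 5. It is neither. Section D names no day and defers to the times given elsewhere in the protocol.

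**Section 7.5.3 already offers better measures.** This is true: dose-interval AUC is listed and modelling is allowed, so the PK objective does not hang on AUClast. But AUClast is still a listed output, and for veliparib it would be wrong as defined.

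**Inflated half-life is not inevitable.** Also true. Section 7.5.3 neither requires nor excludes the 24-hour point in the slope, so the inflation is conditional. The AUClast problem is not.

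**Weight.** The biomarker comparisons are labelled exploratory in a 20-patient pilot, and the CTC wording may be left over, since Section 3.0 already speaks of plasma DNA. That limits the harm, but the objective still needs correcting.

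**Conclusion.** The point holds in three parts of unequal strength.

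1. The CTC part of a secondary objective has no sample behind it. This rests on Section 6.3, the 6.6 schedule and Appendix E; Figure 7 could not be read in the copy used.
2. Cycle 2 PK is an unresolved conflict between Sections 6.3, 6.6 and 7.5.3, not a proven absence.
3. Veliparib AUClast describes neither one dose nor two. That follows from the schedule alone. Its size (1.30-1.37 and 0.69-0.77) depends on the one-compartment assumption and the half-life and Tmax in Section 2.5.

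Lapatinib is not affected by the third part: it is dosed once daily, so 24 hours is its dosing interval. The primary safety endpoint is untouched. The changes should be made, but nothing here undermines the trial's main purpose.

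**What to change.** - **CTCs.** Remove the CTC analyses from Sections 1.2, 6.3 (M30 in CTCs), 7.0, 7.2 and 7.5.2, or name ptDNA in their place if that is what the sponsor intends. Either choice amends a stated secondary objective and needs IRB approval under Section 8.1. Keep the M30 analyses.
- **PK cycles.** Reconcile Section 6.3, the 6.6 mark with footnote 4, and Section 7.5.3. If PK is Cycle 1 only, limit the 7.5.3 parameters to Cycle 1, and keep the optional pre-dose plot only for weeks with a confirmed pre-dose PK sample.
- **Veliparib AUC.** Treat each 24-hour sample as a trough after the second dose and exclude it from AUClast, the terminal slope and AUC to infinity. Report AUC 0-8 h. Base exposure on the planned dose-interval AUC (0-12 h), with 8-12 h extrapolated and the extrapolated share reported, using the recorded dose and sample times.
- **Veliparib half-life and clearance.** State that individual half-life and AUC to infinity from the 4, 6 and 8 h samples are imprecise. Prefer the compartmental or population model that 7.5.3 already allows, fitted with actual dose times.

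Cost: an amendment, some extra analysis work, and the loss of the CTC outputs and possibly the Cycle 2 outputs. None of these changes requires a new sample or a change in dosing.

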2.0 BACKGROUND AND RATIONALE

2.1 “Triple Negative” Breast Cancer Has a Poor Prognosis

Breast cancer is the most commonly diagnosed cancer and the second leading cause of cancer deaths in American women. Despite recent advances in breast cancer therapy, metastatic disease remains incurable. One of the reasons for the lack of cure has been the inability to select subsets of patients most likely to benefit from specific therapies.

The use of modern genomic techniques has significantly enhanced our understanding of breast cancer biology. Thus, five distinct breast cancer tumor subsets have been recognized, including hormone receptor (HR) positive luminal A and B, human epidermal growth receptor 2 (HER-2-Neu) positive, "normal"-like, and basal-like.^{1,2} Basal-like breast cancer (BBC) is typically TNBC, often demonstrates overexpression of the epidermal growth factor receptor-1 (EGFR1), is positive for cytokeratins 5/6/17, and is typically high grade.³⁻⁵ TNBC is a “special clinical interest” cancer because it represents a significant proportion of breast cancer patients (10-20%), has a very poor prognosis in a significant proportion of patients, and as yet, no targeted approach to therapy has been found.

Conforti and colleagues characterized the use of immunohistochemical analysis in the identification of BBC; in 800 breast cancer specimens from a single institution, triple-negative staining had positive and negative predictive values of 67% and 99%. This finding suggests that while not all TNBC are BBC, non-TNBC are almost never BBC.^{6,7} Thus, BBC comprise the majority of the tumors that fit the triple negative phenotype. These cancers are more commonly found in African American women, particularly pre-menopausal, as well as in individuals who harbor a deleterious mutation in the BRCA1 gene.⁸

In addition, Pienpol and her team have recently found that TNBC is a highly diverse group of cancers, and that subtyping may be necessary to better identify molecular-based therapies.⁹ In her study, they analyzed gene expression profiles from 21 breast cancer data sets and identified 587 TNBC cases. Cluster analysis clearly identified 6 TNBC subtypes displaying unique gene expression and ontologies, including 2 basal-like (BL1 and BL2), an immune-modulatory (IM), a mesenchymal (M), a mesenchymal stem-like (MSL), and a luminal androgen receptor (LAR) subtype. Further, genomic expression analysis allowed them to identify TNBC cell line models representative of these subtypes. Predicted "driver" signaling pathways were pharmacologically targeted in these cell line models as proof of concept that analysis of distinct gene expression signatures can inform therapy selection. Thus, if validated, these data may be useful in biomarker selection, drug discovery, and clinical trial design that will enable alignment of TNBC patients to appropriate targeted therapies.

Harris et al. retrospectively evaluated 474 patients with advanced breast cancer enrolled in the CALGB trial 9342 who received paclitaxel in three different schedules.¹⁰ Of the 136 patients in this study for whom complete biomarker data were available, 44 patients had tumors that were triple negative. They found that the majority of these patients had overexpression of p53, and the majority of them were African-American. The response rate to chemotherapy observed in these patients was 26% (compared to 23% in other breast cancer subtypes), but the time to progression (TTP) was 2.8 months (compared to 4.5 months for other breast cancer subtypes), and the overall survival (OS) was 8.6 months (compared to 12.8 months for other breast cancer subtypes).

A similar retrospective analyses has been published including patients enrolled in different neoadjuvant clinical trials at the MDACC.¹¹ In this retrospective evaluation they found that 258 out of 1143 (23%) were triple negative. Interestingly, the TNBC patients had a higher pathological complete response (pCR) (25%) compared with other breast cancer subtypes (11%). However, the 5-year OS was lower for those patients with TNBC (66%) as compared with other subtypes of breast cancer (83%); clearly the best 5-year OS was observed in those patients that had a pCR. The authors concluded that triple negative expression constitutes an independent unfavorable prognostic factor with regard to overall survival unless achieving pCR after neo-adjuvant therapy.

Carey et al. retrospectively examined the relationship of neoadjuvant chemotherapy response to outcome among breast cancer subtypes.¹² They also found that triple negative tumors are more sensitive to anthracycline-based neoadjuvant chemotherapy than other types of breast cancers. Patients that had pCR to chemotherapy (27%) had a good prognosis regardless the subtype (including the triple negative subtype). However, the overall poorer prognosis of triple negative

was due to the higher likelihood of relapse (73%) in those patients in whom pathologic CR was not achieved.

Nam et al. from the National Cancer Center in Korea reported that women with TNBC have a higher risk of brain metastases than other breast cancer types.¹³ The study included 805 patients with advanced breast cancer who were treated between 2001 and 2006. Patients with TNBC had the highest rate of brain metastases (37%), the lowest survival following brain metastasis, and the lowest OS.

Thus, given the lack of effective therapy (especially targeted therapy) in patients diagnosed with TNBC and the poor prognosis associated with it, new therapies for these patients are needed. As described, therapeutic strategies based on functional molecular abnormalities in tumor cells are warranted.

